8 STUDY ASSESSMENTS AND PROCEDURES

8.1 EFFICACY ASSESSMENTS

Inclusion and exclusion criteria will be determined at the initial session, including concomitant therapies, medical history, and diagnosis, to ensure that participants are diagnosed with SLE, with low suicide risk, and free of benzodiazepines and anticonvulsant medications.

[figure not shown]
8.1.1 PHYSIOLOGICAL CHANGES

1. Resting state EEG (RSEEG) recordings will be completed at several times during the course of the study. On Day 1 and Day 5 of the intervention week, participants will complete an eyes open RSEEG immediately before and after the 40 minutes of stimulation. This measure is used to determine the immediate after-effects of tACS on brain activity, specifically on alpha oscillation power, as well as provide a before-stimulation RSEEG on these dates to compare the baseline (Day 1) to the final day of stimulation. RSEEG will also be recorded at both follow-up visits, to determine the outlasting effects of stimulation, if any. An eyes closed RSEEG will also be collected on Day 1, Day 5, and at both follow-up visits.
2. Sustained attention task will be performed with EEG recorded. The simple reaction time task requires participants to initiate a trial by pressing a button and then when prompted push a different button. In the five-choice serial reaction time task, the task is identical except that the participant is prompted to push one of five different buttons. This task measures sustained attention during the delay period of the task between task initiation and the probe appearing.
3. Selective attention task will be performed with EEG recorded. In this task, participants are instructed to orient attention to either the left or right visual field, or to both. Then, two low contrast Gabor wavelet stimuli are displayed on the screen in the left and right visual field. Each Gabor wavelet is oriented to the left or right. Finally, participants are probed as to the orientation (left or right) of the Gabor wavelet in one visual field. The attention cue to the left or right visual field is 80% predictive of which stimuli will be texted by the probe. Selective attention is the ability to improve performance with a predictive cue relative to an informative cue or an incongruent cue.
4. Working memory EEG task will be completed prior to stimulation on Day 1 and Day 5 of stimulation, as well as at both follow-up visits. In the working memory task (WM), participants must encode the color and spatial location of centrally presented squares. After a delay period with a centrally presented fixation cross, a colored square is displayed at a spatial location and participants must determine if this probe stimuli matches the encoded stimuli. By varying the number of stimuli that must be encoded, we will drive WM capacity demands that have been previous demonstrated to evoke a systematic increase in frontal theta oscillations (Jensen & Tesche, 2002) This is to assess if there are any changes in cognition from the intervention.

8.1.2 PAIN EVALUATIONS

1. The Pain Catastrophizing Scale will be assessed at baseline on Day 1 of stimulation and the 3 month follow-up. This is a questionnaire to assess self-reported pain.

2. The Comparative Pain Scale Chart will be administered at baseline, Day 1 through Day 5 of stimulation, both follow-up visits, and the 3 month follow up. This is a visual scale to assess self-reported pain.

To protect our participants during COVID-19, the assessments listed above are offered to be completed using the remote REDCap survey function (PCS and PSC).

8.1.3 CLINICAL EVALUATIONS

1. The Mini International Neuropsychiatric Interview (MINI) is a diagnostic assessment that will be administered at the initial session to determine any psychological comorbidities.
2. The Hamilton Depression Rating Scale 17-item (HDRS17) (Leentjens, Verhey, Lousberg, Spitsbergen, & Wilmink, 2000; Williams, 2001) will be administered during the initial session, day 1 of stimulation (baseline), day 5 of stimulation and at both follow-up visits. This scale is used to monitor the severity of the participant's depression symptoms, as well as determine suicide risk.
3. The Hamilton Anxiety Rating Scale (HAM-A) will be administered at baseline, day 5 of stimulation, and at both follow-up visits. This scale will be used to measure any changes in (possible) comorbid anxiety.
4. The Columbia Suicide Severity Rating Scale (C-SSRS) will be administered at the screening session, baseline, day 5 of stimulation, and at both follow-up visits. The C-SSRS is the gold-standard for assessing suicide risk and will be used, alongside self-report measures, to determine if a patient is at risk of suicide.

To protect our participants during COVID-19, some of the assessments listed above are offered to be collected remotely over the phone or through a UNC approved video platform. These assessments include MINI, HDRS17, HAM-A, and C-SSRS.

8.1.4 PHYSICIAN ASSESSMENTS OF SLE DISEASE ACTIVITY

1. The 2012 Systemic Lupus International Collaborating Clinics (SLICC) criteria for the classification of SLE is used to diagnose lupus based on a weighted scoring system for assessments in the following areas: acute and chronic cutaneous lupus, alopecia, mucosal ulcers, arthritis, serositis, renal, neurologic, hemolytic anemia, thrombocytopenia, leukopenia or lymphopenia, as well as immunologic criteria including ANA,

Lupus Brain		Version 1.8
Protocol		4 March 2022

low complement, Direct Coombs' test, and immunologic disorders as indicated by Anti-dsDNA, Anti-Sm, and Antiphospholipid tests. A participant is eligible if 4 of 17 criteria, including at least one clinical criterion and one immunologic criterion OR biopsy-proven lupus nephritis alone are present. The 1997 America College of Rheumatology (ACR) criteria for the classification of SLE is used to diagnose lupus based on a weighted scoring system for assessments in the following areas: malar rash, discoid rash, photosensitivity, mucosal ulcers, arthritis, serositis, renal disorders, neurologic disorders, hematologic disorders, abnormal ANA, and immunologic disorders. A participant is eligible if 4 of 11 criteria are present. These will be conducted at screening to verify patient eligibility. The patient only has to meet the threshold of the SLICC criteria OR the ACR criteria to be considered eligible for this study.

2. The Systemic Lupus International Collaborating Clinics (SLICC) SLE Damage Index assesses lupus related damage on a weighted scoring system for assessments in the following areas: ocular, neuropsychiatric, renal, pulmonary, cardiovascular, peripheral vascular, gastrointestinal, musculoskeletal, skin, gonadal, endocrine, and malignancy. Damage is defined as nonreversible change, not related to active inflammation, occurring since the onset of lupus as ascertained by clinical assessment and present for at least 6 months unless otherwise stated. Repeat episodes must occur at least 6 months apart to score 2. The same lesions cannot be scored twice. This assessment will be completed by a trained investigator at screening and the 4 week follow-up.
3. The Systemic Lupus Erythematosus Disease Activity Index 2000 (SLEDAI-2K) will be completed by a trained Investigator at screening and at the 4 week follow-up. If the 4 week follow-up visit occurs within 30 days of the screening visit, then a SLEDAI-2k will not be completed at the 4 week follow-up. This questionnaire requires a complete history, physical exam, and lab tests, to measure disease activity in SLE patients. It has 24 items covering 9 organ systems. Scores can range from 0-105 points. A score of 6 is considered clinically important and affects decision to treat.

To protect our participants during COVID-19, some of the assessments listed above are offered to be collected remotely using UNC REDCap database and verified with the study PI during the physical exam. These assessments include the SLICC and SLICC SLE damage index.

8.1.5 SELF-REPORT ASSESSMENTS

1. The 36-Item Short Form Health Survey (SF-36) measures general health using 36 questions. There are 8 individual health "domains" or categories that each receive their own score, and from these 8 individual scores an overall score can be obtained. Overall scores can range from 0-100, with higher scores indicating better overall health.
2. The WHO Disability Assessment Schedule 2.0 (WHODAS 2.0) will be administered at baseline and the 3-month follow up to assess any comorbid disability, which could potentially affect quality of life and/or response to stimulation.
3. The Inventory of Depression and Anxiety Symptoms (IDAS) will be administered at baseline, Day 5 of stimulation, and at both follow-up visits to assess current levels of anxiety and depression.
4. The Positive and Negative Affect Schedule (PANAS) will be administered at every single study session to assess current levels of affect.

5. A blinding questionnaire will be administered on Day 5 of stimulation (Yes or No) to determine if the participant felt that they had received stimulation. Similarly, the study coordinator will also complete a blinding assessment at this point (Yes or No with a free-response space to explain why) to determine if the study coordinator believed the participant received stimulation.

To protect our participants during COVID-19, some of the assessments listed above are offered to be collected remotely using UNC REDCap database. Those assessments include: SF-36, WHODAS 2.0, IDAS, PANAS, and day 5 blinding questionnaire.

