Risk of Injury and Discomfort: The side effects of tACS are mild and transient; in fact, low intensity transcranial current stimulation, such as tACS, has been used for several years without any report of serious side effects ([name] & McCormick, 2010). Furthermore, this stimulation mode has nothing to do with electroconvulsive therapy that applies many orders of magnitude higher stimulation current. Rather, transcranial current stimulation is so weak that it does not cause super-threshold activation of neurons (Khan, Khan, Shankles, & Polissar, 2002). However, tACS does have some mild side effects, such as transient mild tingling, burning, or itching under the electrode sites. In the first part of this study, participants from all three groups reported either absent or mild side effects and there was no difference between the groups with the exception of "flickering lights" (or phosphene, $p = 0.014$) (Alexander et al., 2019). In order to monitor these, we will be administering an adverse effects stimulation questionnaire after each stimulation session to determine whether these effects were experienced and at what intensity. Research personnel present during these sessions will also check in with the participant periodically during the stimulation to see whether they are comfortable. If participant is experiencing severe discomfort (as determined by the adverse effects questionnaire or by self-report), the stimulation will be immediately stopped.

Risks associated with emotional distress in case of incidental findings on structural MRI or a false positive pregnancy test.

Risks associated with venous blood draw include minimal discomfort and/or bruising. Infection, excess bleeding, clotting, and fainting are also possible, although unlikely.

Patients experiencing depression have a higher risk of suicide. We have no evidence that our treatment paradigms will in any way increase this likelihood. In a similar study in patients with major depressive disorder (MDD), 4 participants in the sham/placebo stimulation group experienced an increase in suicidal thoughts and only one of those 4 participants reported suicidal intent. No participants who

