4.2 SCIENTIFIC RATIONALE FOR STUDY DESIGN

This study is a double-blind, randomized, sham-controlled interventional study. The choice of double-blind and randomized for this study is important for the integrity of our data, especially for the clinical assessments. All individuals involved with data collection (as well as all randomized participants) will not know participant assignment until all data has been collected. This will reduce implicit and explicit bias in the data collection process.

In this study, participants will be randomized in to one of three arms: active sham/placebo stimulation, individualized alpha-tACS (usually 8-12Hz), or individualized theta-tACS (alpha frequency minus 4 Hz). We propose that alpha-tACS will be the therapeutic frequency, based on work in our lab demonstrating the effect of 10Hz-tACS on depression (Alexander et al., 2019) and chronic pain (Ahn et al., 2019); whereas, previous work from our lab demonstrates that alpha oscillations exist in an antagonistic relationship with theta oscillations (Stitt et al., 2018). Therefore, theta-tACS was chosen as a control stimulation frequency for this study.

In this design, our sham/placebo stimulation is active, including 80 seconds of stimulation (20 seconds ramp-in to 40 seconds of 10 Hz tACS at 1 mA with 20 seconds of ramp-out). This choice of active sham/placebo is important to mimic the skin sensations and other transient side effects associated with stimulation. Typically, stimulation side effects only last approximately a minute into stimulation; indicating that theoretically sham/placebo stimulation should be difficult to differentiate from verum tACS.

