6.1.2 DOSING AND ADMINISTRATION

The research team will first measure each participant's head using the 10-20 system to determine the electrode locations. Participants will then be fitted with the 3 electrodes for stimulation: two 5x5cm

electrodes placed over F3 and F4, and one 5x7cm electrode placed on Cz. Electrodes will be carbon rubber, with Ten20 conductive paste applied. During stimulation, the participant will be in a relaxed and experimentally-controlled state by watching a nature movie (such as *Reefscapes*). One session of stimulation will be performed per patient per day, for 40 minutes. Before and after the stimulation on Day 1 and Day 5 of stimulation, an eyes open resting state EEG will be performed.

Participants will be randomly assigned to one of three arms; active sham stimulation, individualized alpha-tACS (usually 8-12Hz), or individualized theta-tACS (alpha frequency minus 4 Hz). Active sham stimulation will include 20 seconds of ramp-in to 40 seconds of 10 Hz tACS with a ramp out of 20 seconds for a total of 80 seconds of stimulation. The choice of an active sham is motivated to enhance success of patient blinding by mimicking skin sensations associated with tACS. Alpha- tACS and theta-tACS will have a 20 second ramp-in and ramp-out with 40 minutes of stimulation for a total of 2440 seconds of stimulation. Stimulation waveform is a sine-wave with a zero-to-peak amplitude of 1 mA. In each arm, participants will stay in a relaxed and yet controlled state by watching a nature movie such as "Reefscape" during stimulation.

Stimulation devices will be preprogrammed and codes will be randomized to one of the two experimental arms. Researchers will enter the participant-specific code into the Asus tablet that controls the XCSITE100 device and will monitor participants during the 40 minutes of the stimulation. The study coordinator and/or the research assistant will be thoroughly trained and have trainings documented on the transcranial stimulation device and will be present during all stimulation sessions. To monitor side effects of stimulation an adverse events questionnaire will be administered after each stimulation session.

Adverse Effects Questionnaire:

Transcranial Current Stimulation Questionnaire

Did you experience any of the following? Please circle the appropriate number for each (1-4). In the last column, indicate how related the symptom is to transcranial current stimulation

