6.2.2 BLINDING

This study is designed to be double-blind. This means that the participant and the researchers do not know of each participant's assignment until the completion of all data collection. This is accomplished by the use of the randomization codes described above.

Furthermore, this study utilizes an active sham stimulation. This means that the sham/placebo condition includes some stimulation, mimicking the skin sensations associated with tACS. In our previously concluded trial (Alexander et al., 2019), participants in the sham and 10 Hz tACS groups responded similarly to the blinding questionnaire, indicating that our active sham stimulation successfully blinded the participants.

Additionally, during the initial data analysis phase, [name] will be blinded to whether data and results are from sham vs active treatment in compliance with the UNC School of Medicine Conflict of Interest Committee proposed financial conflict of interest management plan.

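### The Day 5 blinding item asks whether stimulation was received, which is literally true in every arm, so similar Yes rates cannot confirm the blind

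*Combined protocol and SAP*

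**What the plan says.** Section 8.1.5 gives the participant a Yes/No questionnaire on Day 5 whose purpose is "to determine if the participant felt that they had received stimulation". The study coordinator completes a parallel Yes/No item, with free space for a reason, "to determine if the study coordinator believed the participant received stimulation".

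The sham is not current-free. Section 4.2 states that "our sham/placebo stimulation is active, including 80 seconds of stimulation". Section 6.1.2 describes the sham as a ramp-in and 40 seconds of 10 Hz tACS, "with a ramp out of 20 seconds for a total of 80 seconds of stimulation", and the two active arms as ramped "with 40 minutes of stimulation for a total of 2440 seconds of stimulation". Section 6.2.2 gives the reason: "This means that the sham/placebo condition includes some stimulation, mimicking the skin sensations associated with tACS".

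Section 6.2.2 also shows how such a questionnaire is read. In an earlier tACS trial the sham and 10 Hz groups answered alike, and this is taken as evidence that the active sham kept participants blind. Section 9.4 contains no analysis of the blinding data, and blinding does not appear in the objectives table in section 3.

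**The concern.** A blinding check needs answers that can be right or wrong. Here the question, as described, has the same true answer in every arm. A sham participant who noticed the sensation stop after about a minute, and so worked out the allocation, can truthfully say Yes. So can a sham participant who suspects nothing, and anyone on alpha- or theta-tACS. Similar Yes rates are then compatible both with an intact blind and with a broken one.

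The blind matters most for the HDRS17, HAM-A, IDAS and pain scales. The HDRS, IDAS and pain changes enter the secondary correlations (9.1.2, 9.4.3), and clinical measures are followed by arm and session as an exploratory outcome (9.4.8). The coordinator's blind matters too. A coordinator or assistant attends every stimulation session (6.1.2), and the coordinator conducts the remote HDRS17 and HAM-A (4.1). Section 5.5 aims to keep the same team member with each participant.

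A sensory difference between arms is already on record. For side effects in the earlier trial, section 2.3.1 says "there was no difference between the groups with the exception of" flickering lights (p = 0.014).

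**Working it through.** **1. Stimulation per session (6.1.2).** Sham: 20 + 40 + 20 = 80 s. Active: 20 + 40 × 60 + 20 = 2440 s. Both match the protocol. The sham is short (80/2440 = 3.3% of the active duration), but it is real current.

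**2. What a Yes means.** Let *y* be the Yes rate among participants who have not worked out their arm, *k* the share of sham participants who have, and *L* the share of those who still answer the literal question. Then

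P(Yes | sham) = *y* × [1 − *k*(1 − *L*)].

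Take *y* = 0.90 and *k* = 4/9 (assumptions):
- If all of them treat the item as an allocation guess (*L* = 0), the sham rate is 0.90 × 5/9 = 0.50, against 0.90 in the active arms.
- If all of them answer literally (*L* = 1), the sham rate is 0.90, equal to the active arms, whatever *k* is.

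The same degree of unblinding gives either a large difference or none, depending on a reading that the item does not fix.

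**3. What a between-arm comparison can detect.** Sizes: 45/3 = 15 per arm (9.3), so 15 sham v 30 pooled active; and 20 per group (9.2), so 20 v 40. Method: exact power of Fisher's test on the Yes proportion at 0.05, two-sided (sidedness is assumed; 9.4.1 does not state it). The documents give no Yes rates, so those below are assumptions.

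| Yes rate, sham / active | 15 v 30 | 20 v 40 |
|---|---|---|
| 100% / 100% | 0.00 | 0.00 |
| 90% / 95% | 0.06 | 0.09 |
| 80% / 95% | 0.30 | 0.41 |
| 70% / 90% | 0.34 | 0.44 |
| 50% / 90% | 0.80 | 0.90 |
| 30% / 90% | 0.985 | 0.998 |

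Large differences are detectable. Near the ceiling, where a sham built to be felt may put the answers, almost nothing is.

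**4. Scoring the present item as a guess.** Count Yes as a guess of active. The arm-wise blinding index is then 2*p* − 1 in the active arms and 1 − 2*p* in sham, where *p* is the Yes rate. At 90% Yes in every arm it is +0.8 and −0.8, summing to 0. That pattern arises equally if everyone believes they are on active treatment or if everyone simply reports feeling the current.

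**The case against.** The strongest reply is that the comparison between arms is what counts, not whether each answer is true. If Yes rates differ, the arms could be told apart, and section 6.2.2 uses the questionnaire in exactly this comparative way. That stands. A reader might infer that the item can show nothing about the blind; the table shows otherwise for large differences, and the coordinator's free-text reason adds information.

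Second, section 8.1.5 states the purpose of the form but not its wording. Participants may take stimulation to mean real treatment rather than sham, and a coordinator who knows that the sham carries current could hardly read it any other way. This also stands, but it shows that the item is ambiguous, not that it is sound. A reader might go further and infer that similar answers are guaranteed by construction, or that the earlier trial's result was. The documents give neither that trial's wording nor its response rates, so this is not supported.

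Third, the consequences are limited. The primary outcome is EEG alpha power, the secondary analyses are correlations rather than comparisons of symptoms by arm, and theta-tACS matches alpha-tACS in duration and amplitude. All of this is correct and bounds the concern. The side-effects questionnaire after each session also records sensations, though it does not record guesses. The flickering-lights result shows a sensory difference, not that anyone was unblinded.

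**Conclusion.** The point holds in a limited form. As described, the item is ambiguous and one-directional: it may reveal gross unblinding, but it cannot confirm that the blind held. Under the assumed rates, power against a sham-active difference runs from 0.00–0.06 near the ceiling to 0.80–0.985 for differences of 40 to 60 percentage points (15 v 30).

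The fact that Yes is literally true in every arm rests on the protocol's own figures. How participants would read the question, and what Yes rates to expect, are unknown.

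The documents do not support the inference that the blind will fail, or that the primary EEG analysis is undermined. This is an ancillary assessment, not an endpoint. It is still worth correcting, because it is the only direct check on the blind that the text describes and no analysis of it is specified.

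**What to change.** On Day 5, replace or supplement the item with an allocation guess for both participant and coordinator: active treatment, sham, or do not know, followed by a confidence rating. Keep the coordinator's free-text reason. The present Yes/No item can stay for comparison with the earlier trial.

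Add a short paragraph to section 9.4: tabulate guess by true arm, report an arm-wise blinding index (proportion guessing correctly minus proportion guessing wrongly) with a confidence interval, and state that similar Yes rates will not be read as proof of blinding. The index will be imprecise. Its variance is at most 1/n, so the 95% half-width can reach 1.96/√15 = 0.51 in sham and 1.96/√30 = 0.36 in the pooled active arms. It should be reported as an estimate, not as pass or fail.

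The cost is one or two extra questions. Day 5 guesses may partly reflect symptom change and should be read with that in view. A guess after the first session would separate early sensory cues from later symptom change, but it is optional. If used, it should not describe the brief-stimulation sham, because that would tell participants what to look for in the four remaining sessions.
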